#### 9.1.3.1 Blood Pressure Management

Blood pressure and HR will be measured with the subject in a sitting position after 5 minutes of rest. The procedure for standardized measurement of BP is detailed in [Appendix 2](#).

If the mean BP measure is  $>130/80$  mmHg (determined by the mean of the second and third repeats of 3 readings), the subject's BP will be managed per local practice. If the BP remains uncontrolled with the maximal doses of first- and second-line antihypertensive therapies referenced in [Appendix 1](#), then the Investigator should contact the Medical Monitor to consider dose adjustment of the study treatment. See [Section 7.7, Increased Blood Pressure](#) for management of increased BP.

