## Appendix 1 Drug Therapy for the Treatment of Hypertension

Antihypertensive drug therapy for subjects who either have hypertension at screening or who develop hypertension while on study treatment may include the following:

- Dihydropyridine calcium channel blockers (e.g., amlodipine, nifedipine)
- Alpha-1-adrenergic blocking agents (e.g., doxazosin)
- Alpha-beta-blockers (e.g., carvedilol, labetalol)
- Thiazide diuretics (e.g., chlorthalidone or hydrochlorothiazide)

Excluded Drugs: While the ARBs and ACE inhibitors may also be effective in calcineurin inhibitor-associated hypertension, their dose adjustment or commencement is not permitted after the screening period (including stabilization visits) in this trial (see [Section 7.6.1, Prohibited Medications](#)).

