### Recommended First and Second Line Therapies for Treatment of Hypertension

Titrate the following according to the timeframe given in the respective drug label:

First Line - select from one of the following:

- Amlodipine, 5 mg daily to achieve BP <140/90 mmHg; titrate to 10 mg daily if satisfactory results not obtained within 2 weeks
- Nifedipine XL, 30 mg daily; titrate to 60 mg and possibly 90 mg daily within 2 weeks
- 12.5 to 25 mg/day of chlorthalidone or hydrochlorothiazide

Second Line - may add from among the following to the first line therapy if a partial response is obtained:

- Labetalol, 100 mg BID; titrate to 200 mg BID, then 300 mg BID

Note: If the BP remains uncontrolled with the above-referenced maximum doses of first and second-line antihypertensive therapies, reduction of study treatment dose may be considered or it may be decided to discontinue study treatment and utilize antihypertensive therapies to achieve control of BP.

**If at any time, in the judgment of the treating physician in consultation with the Medical Monitor, the response to treatment is inadequate, the study treatment may be discontinued.**

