- In the case of uncontrolled hypertension (systolic BP >165 mmHg or diastolic >105 mmHg on two successive measurements), the addition of a diuretic or calcium channel blocker only are permitted, together with dose decreases or interruption of study treatment per the instructions in [Section 7.7, Increased Blood Pressure](#).

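### Above 165/105 mmHg, Appendix 5 limits added antihypertensives to two classes, which Appendix 1, Section 7.7 and the Section 9.1.3.1 condition do not match

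*Combined protocol and SAP*

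**What the plan says.** Four places in the protocol govern how raised BP is treated.

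- **Appendix 5**, last item. The trigger is "systolic BP >165 mmHg or diastolic >105 mmHg on two successive measurements", with no mention of symptoms. At that level "the addition of a diuretic or calcium channel blocker only are permitted". The same sentence couples these additions with lowering or interrupting the study drug and refers the reader to Section 7.7 for how to do so.
- **Appendix 1.** Its scope is stated as "Antihypertensive drug therapy for subjects who either have hypertension at screening or who develop hypertension while on study treatment may include the following". The list has four classes: dihydropyridine calcium channel blockers, alpha-1-blockers, alpha-beta-blockers and thiazide diuretics. First line is amlodipine, nifedipine XL or a thiazide-type drug. After a partial response a second-line drug may be added, and the only one given is "Labetalol, 100 mg BID; titrate to 200 mg BID, then 300 mg BID". The appendix sets no BP ceiling and does not refer to Appendix 5. A closing note allows study-drug reduction or discontinuation if BP stays uncontrolled on the maximum first- and second-line doses.
- **Section 9.1.3.1.** Mean BP above 130/80 mmHg is managed by local practice. If BP remains "uncontrolled with the maximal doses of first- and second-line antihypertensive therapies" of Appendix 1, the investigator contacts the Medical Monitor to consider adjusting the study drug.
- **Section 7.7.** If no further antihypertensive adjustment is possible, the case goes to the Medical Monitor. If BP exceeds 165 systolic or 105 diastolic with symptoms, study treatment is withheld and the subject is treated by local practice and the investigator's judgment. No drug class is excluded there.

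**The concern.** Increased BP is one of the two dose-related toxicities of calcineurin inhibitors named in Section 1.2.4, and Section 2.1 allows a higher dose in Cohort 2. Sites therefore need one workable rule for severe hypertension. As written, the list of drugs that may be added becomes shorter at the highest pressures on one page and stays unchanged on another. Two further passages make a study-drug decision depend on a drug that the first page does not allow to be added.

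What is at stake is uniform handling. Two sites could each follow a page of the protocol and still treat the same subject differently, both in the antihypertensive given and in the point at which study-drug adjustment is considered. With about 20 subjects planned (Section 13.2), a few such differences would be visible in the concomitant-medication and exposure summaries.

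**Working it through.** No arithmetic applies, and the plan gives no figure to reproduce. The check sets the passages side by side and follows particular subjects through them.

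**Step 1: compare the drug lists.**

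| Class in Appendix 1 | Place in Appendix 1 | May be added under Appendix 5 above 165/105 on two readings? |
|---|---|---|
| Dihydropyridine calcium channel blocker | First line | Yes |
| Thiazide diuretic | First line | Yes |
| Alpha-1-blocker | Listed, no line given | No |
| Alpha-beta-blocker (includes labetalol) | Sole second line | No |

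Two of four classes fall outside Appendix 5, and one of them contains the only second-line drug.

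**Step 2: a subject without symptoms.** Take two successive readings above the threshold, a partial response to a first-line drug, and no labetalol so far.

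- Appendix 1 allows labetalol to be added. Appendix 5 does not, because it is neither a diuretic nor a calcium channel blocker.
- If the site follows Appendix 5, the subject never receives second-line therapy. The condition in Section 9.1.3.1 and in the Appendix 1 note, failure on maximal first- *and* second-line therapy, cannot then be met.
- Appendix 5 itself couples the additions with dose decrease or interruption and sends the reader to Section 7.7. That section contains no dose-decrease instruction, and its withholding rule requires symptoms, which this subject does not have.

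**Step 3: the same subject with symptoms.** Section 7.7 withholds study drug and leaves treatment to local practice, with no class limit. Appendix 5 has no symptom condition, so its two-class limit applies to the same subject at the same time. The two do not agree.

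**Step 4: a subject already on labetalol.** Appendix 5 restricts only additions. It does not address continuing or titrating an existing drug. The Section 9.1.3.1 condition may then be reachable, so the difficulty in Step 2 is confined to subjects not yet on labetalol.

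**Step 5: other routes to a study-drug change.**

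- Section 7.1.2.1 lets the investigator hold doses.
- Section 7.7 withholds drug when symptoms are present, and refers the case to the Medical Monitor when antihypertensive options run out.
- Appendix 1 allows discontinuation at any time, in consultation with the Medical Monitor, if the response is inadequate.
- Appendix 5 itself names dose decrease or interruption.

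Only the condition shared by Section 9.1.3.1 and the Appendix 1 note is out of reach.

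**The case against.** The best defence is that the conflict is narrow and the protocol supplies ways round it.

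- *Appendix 5 is a special rule for severe hypertension that overrides the general list.* This is a possible reading, but no passage says so, and Appendix 1 has no BP ceiling.
- *The word* only *was meant to rule out ACE inhibitor and ARB changes, which the preceding item of Appendix 5 concerns.* This is plausible as intent. The words are not limited in that way, however, and Appendix 1 already excludes those changes separately.
- *Section 7.6.2 lets sites clear unlisted treatments with the Medical Monitor.* This stands in part, because it gives sites someone to ask. It deals with treatments the list does not mention and does not remove an express limit.
- *Appendix 1 is permissive and does not instruct anyone to give labetalol.* This is correct. The conflict is between a permission and a restriction, together with a condition that presupposes the permission was used.

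A reader might also infer two stronger things. The first is that study-drug adjustment is blocked altogether for these subjects. The routes in Step 5 show that it is not, and Section 9.1.3.1 itself speaks only of considering an adjustment. The second is that a subject given labetalol would drop out of the per-protocol set. Section 13.3.3 leaves the definition of major violations to the SAP, and Section 17.1 has deviations graded case by case. Nothing in the documents says an added antihypertensive would count as major.

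**Conclusion.** The passages cannot all be followed for a subject with two successive readings above 165 systolic or 105 diastolic. Two of the four Appendix 1 classes, including its only second-line drug, fall outside what Appendix 5 lets a site add. For such a subject not already on labetalol, the condition in Section 9.1.3.1 and the Appendix 1 note is unreachable under Appendix 5. Separately, the pointer from Appendix 5 to Section 7.7 leads to a section with no dose-decrease instruction, a symptom requirement that Appendix 5 lacks, and no class limit.

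This rests on reading *only* in Appendix 5 literally and on the absence of any statement about which passage takes precedence. The documents do not say how many subjects would be affected. The primary analysis uses the intent-to-treat set, all analyses are descriptive (Section 13.9), and no endpoint definition or stated figure changes. It is an inconsistency in a safety rule that should be corrected. It is not a flaw in the analysis.

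**What to change.** Reconcile Appendix 1, Appendix 5, Section 7.7 and Section 9.1.3.1 so that three things agree:

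1. which antihypertensive additions are permitted at each BP level, with and without symptoms;
2. the condition for considering study-drug adjustment, so that it can be met using only the permitted drugs;
3. the cross-reference from Appendix 5, so that it points to text containing the dose-decrease and interruption instructions it relies on.

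Whether the answer is one list or a list tiered by BP, and which classes it contains, is for the sponsor's clinicians. The cost is a wording change in these four places at the next amendment and a clarification note to sites. No data collection, visit or analysis has to change.

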## Appendix 6 Summary of Treatment and Food Restrictions

Treatment	Washout Period	During Treatment	Reason
Immunosuppressants other than those allowed by protocol	30 days	Prohibited	Interferes with study efficacy endpoints
Aminoglycosides Amphotericin B Melphalan Ketoconazole Rifampin	14 days	Prohibited	May potentiate toxicity
NSAIDs chronic dosing (>7 consecutive days)	Prohibited	Prohibited	May potentiate nephrotoxicity
P-gp substrates	To be monitored	To be monitored	Drug-drug interaction
P-gp inhibitors	To be discussed with Medical Monitor	To be discussed with Medical Monitor	Drug-drug interaction
Androgenic steroids Cimetidine Fluconazole, itraconazole Macrolide antibiotics (azithromycin, clarithromycin, erythromycin) Metoclopramide Barbiturates and derivatives Carbamazepine Octreotide acetate Phenytoin Sulfadimidine (intravenous) Theophylline	To be discussed with Medical Monitor	To be discussed with Medical Monitor	Drugs interfering with voclosporin metabolism
ACEIs and ARBs	Stable dose for at least 2 weeks prior to baseline	Change or commencement prohibited	Interfere with primary endpoint assessment
Foods Grapefruit and grapefruit juice	24 hours	Prohibited	May affect the metabolism of voclosporin

Notes: ACEI = Angiotensin converting enzyme inhibitor; ARB = Angiotensin receptor blocker; NSAID = Non-steroidal anti-inflammatory drug; P-gp = P-glycoprotein.

## **Appendix 7 PROMIS QoL Assessment**

The PROMIS QoL assessment includes three questionnaires:

- Physical Function – Short Form 10a (PROMIS® Item Bank v2.0)
- Fatigue – Short Form 8a (PROMIS® Item Bank v1.0)
- Pain Interference – Short Form 8a (PROMIS® Item Bank v1.0)

## **Appendix 8 KDQOL-SF™ QoL Assessment Version 1.3**

---

# Your Health – *and* – Well-Being

## Kidney Disease and Quality of Life (KDQOL-SF™ 1.3)

This survey asks for your views about your health. This information will help keep track of how you feel and how well you are able to do your usual activities.

***Thank you for completing these questions!***

# **Study of Quality of Life For Patients on Dialysis**

---

---

# Your Health

This survey includes a wide variety of questions about your health and your life. We are interested in how you feel about each of these issues.

1. In general, would you say your health is: [Mark an  in the one box that best describes your answer.]

Excellent	Very good	Good	Fair	Poor
▼	▼	▼	▼	▼
 1	 2	 3	 4	 5

2. Compared to one year ago, how would you rate your health in general now?

Much better now than one year ago	Somewhat better now than one year ago	About the same as one year ago	Somewhat worse now than one year ago	Much worse now than one year ago
▼	▼	▼	▼	▼
 1	 2	 3	 4	 5

**3. The following items are about activities you might do during a typical day. Does your health now limit you in these activities? If so, how much? [Mark an  in a box on each line.]**

	Yes, limited a lot ▼	Yes, limited a little ▼	No, not limited at all ▼
a Vigorous activities , such as running, lifting heavy objects, participating in strenuous sports .....	 1.....	 2.....	 3
b Moderate activities , such as moving a table, pushing a vacuum cleaner, bowling, or playing golf .....	 1.....	 2.....	 3
c Lifting or carrying groceries .....	 1.....	 2.....	 3
d Climbing several flights of stairs .....	 1.....	 2.....	 3
e Climbing one flight of stairs.....	 1.....	 2.....	 3
f Bending, kneeling, or stooping .....	 1.....	 2.....	 3
g Walking more than a mile .....	 1.....	 2.....	 3
h Walking several blocks .....	 1.....	 2.....	 3
i Walking one block .....	 1.....	 2.....	 3
j Bathing or dressing yourself.....	 1.....	 2.....	 3

**4. During the past 4 weeks, have you had any of the following problems with your work or other regular daily activities as a result of your physical health?**

Yes ▼	No ▼
----------	---------

- a Cut down the amount of time you spent on work or other activities .....  1 .....  2
- b Accomplished less than you would like.....  1 .....  2
- c Were limited in the kind of work or other activities .....  1 .....  2
- d Had difficulty performing the work or other activities (for example, it took extra effort).....  1 .....  2

**5. During the past 4 weeks, have you had any of the following problems with your work or other regular daily activities as a result of any emotional problems (such as feeling depressed or anxious)?**

Yes ▼	No ▼
----------	---------

- a Cut down the amount of time you spent on work or other activities .....  1 .....  2
- b Accomplished less than you would like.....  1 .....  2
- c Didn't do work or other activities as carefully as usual.....  1 .....  2

6. During the past 4 weeks, to what extent has your physical health or emotional problems interfered with your normal social activities with family, friends, neighbors, or groups?

Not at all	Slightly	Moderately	Quite a bit	Extremely
▼	▼	▼	▼	▼
 1	 2	 3	 4	 5

7. How much bodily pain have you had during the past 4 weeks?

None	Very mild	Mild	Moderate	Severe	Very severe
▼	▼	▼	▼	▼	▼
 1	 2	 3	 4	 5	 6

8. During the past 4 weeks, how much did pain interfere with your normal work (including both work outside the home and housework)?

Not at all	A little bit	Moderately	Quite a bit	Extremely
▼	▼	▼	▼	▼
 1	 2	 3	 4	 5

**9. These questions are about how you feel and how things have been with you during the past 4 weeks. For each question, please give the one answer that comes closest to the way you have been feeling.**

**How much of the time during the past 4 weeks...**

	All of the time ▼	Most of the time ▼	A good bit of the time ▼	Some of the time ▼	A little of the time ▼	None of the time ▼
--	----------------------------	-----------------------------	--------------------------------------	-----------------------------	---------------------------------	-----------------------------

- |   |  |                                 |                                 |                                 |                                 |                                 |                            |
|---|--|---------------------------------|---------------------------------|---------------------------------|---------------------------------|---------------------------------|----------------------------|
| a | Did you feel full of pep?.....   |  1..... |  2..... |  3..... |  4..... |  5..... |  6 |
| b | Have you been a very nervous person? .....                               |  1..... |  2..... |  3..... |  4..... |  5..... |  6 |
| c | Have you felt so down in the dumps that nothing could cheer you up?..... |  1..... |  2..... |  3..... |  4..... |  5..... |  6 |
| d | Have you felt calm and peaceful?.....                                    |  1..... |  2..... |  3..... |  4..... |  5..... |  6 |
| e | Did you have a lot of energy? .....                                      |  1..... |  2..... |  3..... |  4..... |  5..... |  6 |
| f | Have you felt downhearted and blue? .                                    |  1..... |  2..... |  3..... |  4..... |  5..... |  6 |
| g | Did you feel worn out?..   |  1..... |  2..... |  3..... |  4..... |  5..... |  6 |
| h | Have you been a happy person?.....                                       |  1..... |  2..... |  3..... |  4..... |  5..... |  6 |
| i | Did you feel tired? .....  |  1..... |  2..... |  3..... |  4..... |  5..... |  6 |

**10. During the past 4 weeks, how much of the time has your physical health or emotional problems interfered with your social activities (like visiting with friends, relatives, etc.)?**

All of the time	Most of the time	Some of the time	A little of the time	None of the time
▼	▼	▼	▼	▼
 1	 2	 3	 4	 5

**11. Please choose the answer that best describes how true or false each of the following statements is for you.**

	Definitely true	Mostly true	Don't know	Mostly false	Definitely false	
	▼	▼	▼	▼	▼	
a	I seem to get sick a little easier than other people .....	 1 .....	 2 .....	 3 .....	 4 .....	 5
b	I am as healthy as anybody I know ....	 1 .....	 2 .....	 3 .....	 4 .....	 5
c	I expect my health to get worse .....	 1 .....	 2 .....	 3 .....	 4 .....	 5
d	My health is excellent.....	 1 .....	 2 .....	 3 .....	 4 .....	 5

# Your Kidney Disease

## 12. How true or false is each of the following statements for you?

	Definitely true ▼	Mostly true ▼	Don't know ▼	Mostly false ▼	Definitely false ▼				
a My kidney disease interferes too much with my life .....	 1	.....	 2	.....	 3	.....	 4	.....	 5
b Too much of my time is spent dealing with my kidney disease .....	 1	.....	 2	.....	 3	.....	 4	.....	 5
c I feel frustrated dealing with my kidney disease .....	 1	.....	 2	.....	 3	.....	 4	.....	 5
d I feel like a burden on my family .....	 1	.....	 2	.....	 3	.....	 4	.....	 5

**13. These questions are about how you feel and how things have been going during the past 4 weeks. For each question, please give the one answer that comes closest to the way you have been feeling.**

**How much of the time during the past 4 weeks...**

	None of the time ▼	A little of the time ▼	Some of the time ▼	A good bit of the time ▼	Most of the time ▼	All of the time ▼
a Did you isolate your- self from people around you? .....	 1 .....	 2 .....	 3.....	 4 .....	 5.....	 6
b Did you react slowly to things that were said or done?.....	 1 .....	 2 .....	 3.....	 4 .....	 5.....	 6
c Did you act irritable toward those around you?.....	 1 .....	 2 .....	 3.....	 4 .....	 5.....	 6
d Did you have difficulty concentrating or thinking?.....	 1 .....	 2 .....	 3.....	 4 .....	 5.....	 6
e Did you get along well with other people? .....	 1 .....	 2 .....	 3.....	 4 .....	 5.....	 6
f Did you become confused? .....	 1 .....	 2 .....	 3.....	 4 .....	 5.....	 6

**14. During the past 4 weeks, to what extent were you bothered by each of the following?**

	Not at all bothered	Somewhat bothered	Moderately bothered	Very much bothered	Extremely bothered
	▼	▼	▼	▼	▼
a Soreness in your muscles?.....	 1 .....	 2 .....	 3 .....	 4 .....	 5
b Chest pain? .....	 1 .....	 2 .....	 3 .....	 4 .....	 5
c Cramps? .....	 1 .....	 2 .....	 3 .....	 4 .....	 5
d Itchy skin?.....	 1 .....	 2 .....	 3 .....	 4 .....	 5
e Dry skin?.....	 1 .....	 2 .....	 3 .....	 4 .....	 5
f Shortness of breath? .....	 1 .....	 2 .....	 3 .....	 4 .....	 5
g Faintness or dizziness?.....	 1 .....	 2 .....	 3 .....	 4 .....	 5
h Lack of appetite?...	 1 .....	 2 .....	 3 .....	 4 .....	 5
i Washed out or drained? .....	 1 .....	 2 .....	 3 .....	 4 .....	 5
j Numbness in hands or feet?.....	 1 .....	 2 .....	 3 .....	 4 .....	 5
k Nausea or upset stomach?.....	 1 .....	 2 .....	 3 .....	 4 .....	 5
l (Hemodialysis patient only) Problems with your access site? ...	 1 .....	 2 .....	 3 .....	 4 .....	 5
m (Peritoneal dialysis patient only) Problems with your catheter site?..	 1 .....	 2 .....	 3 .....	 4 .....	 5

# Effects of Kidney Disease on Your Daily Life

15. Some people are bothered by the effects of kidney disease on their daily life, while others are not. How much does kidney disease bother you in each of the following areas?

	Not at all bothered	Somewhat bothered	Moderately bothered	Very much bothered	Extremely bothered
	▼	▼	▼	▼	▼
a Fluid restriction?....	 1	.....  2	.....  3	.....  4	.....  5
b Dietary restriction?.	 1	.....  2	.....  3	.....  4	.....  5
c Your ability to work around the house? .....	 1	.....  2	.....  3	.....  4	.....  5
d Your ability to travel? .....	 1	.....  2	.....  3	.....  4	.....  5
e Being dependent on doctors and other medical staff?.....	 1	.....  2	.....  3	.....  4	.....  5
f Stress or worries caused by kidney disease? .....	 1	.....  2	.....  3	.....  4	.....  5
g Your sex life? .....	 1	.....  2	.....  3	.....  4	.....  5
h Your personal appearance? .....	 1	.....  2	.....  3	.....  4	.....  5

The next three questions are personal and relate to your sexual activity, but your answers are important in understanding how kidney disease impacts on people's lives.

**16. Have you had any sexual activity in the past 4 weeks?**

**(Circle One Number)**

No .....1

If no, please skip to Question 17

Yes .....2

**How much of a problem was each of the following in the past 4 weeks?**

	Not a problem	A little problem	Somewhat of a problem	Very much a problem	Severe problem					
a	Enjoying sex? .....	 1	.....	 2	.....	 3	.....	 4	.....	 5
b	Becoming sexually aroused? .....	 1	.....	 2	.....	 3	.....	 4	.....	 5

**17. For the following question, please rate your sleep using a scale ranging from 0 representing “very bad” to 10 representing “very good.”**

**If you think your sleep is half-way between “very bad” and “very good,” please mark the box under the number 5. If you think you sleep is one level better than 5, mark the box under 6. If you think your sleep is one level worse than 5, mark the box under 4 (and so on).**

**On a scale from 0 to 10, how would you rate your sleep overall?  
[Mark an  in one box.]**

Very bad											Very good
▼											▼
0	1	2	3	4	5	6	7	8	9	10	
											

**18. How often during the past 4 weeks did you...**

	None of the time	A little of the time	Some of the time	A good bit of the time	Most of the time	All of the time
a Awaken during the night and have trouble falling asleep again?.....	 1	 2	 3	 4	 5	 6
b Get the amount of sleep you need?.....	 1	 2	 3	 4	 5	 6
c Have trouble staying awake during the day?...	 1	 2	 3	 4	 5	 6

**19. Concerning your family and friends, how satisfied are you with...**

	Very dissatisfied	Somewhat dissatisfied	Somewhat satisfied	Very satisfied
a The amount of time you are able to spend with your family and friends?.....	 1	 2	 3	 4
b The support you receive from your family and friends?.....	 1	 2	 3	 4

